5.1.7.2.4 Time to Reach Acceptable Pain

Time to reach acceptable pain (TTAP) will be defined as the time (hours) from baseline subject symptom self-assessment date and time (Day 1 Visit 1, Pain Perception) to the first report of post-baseline acceptable pain. If that event never occurs, the time will be censored with the last response. If there are no post-baseline assessments collected, then the time will be censored with baseline subject symptom self-assessment.

TTAP will be listed and analyzed with cumulative distributions (F(t)) and the corresponding summaries using cumulative incidence estimates $(\hat{F}(t) = 1 - \hat{S}(t))$ based on the Kaplan-Meier survival estimates $(\hat{S}(t))$. The 95% confidence limits $(\hat{F}_L(t), \hat{F}_U(t))$ for point estimates will be evaluated using 95% confidence limits for survival estimates $(\hat{S}_L(t), \hat{S}_U(t))$ as follows:

$$\hat{F}_L(t) = 1 - \hat{S}_U(t); \ \hat{F}_U(t) = 1 - \hat{S}_L(t).$$

The comparison between treatment groups will be done by the Log-Rank test.

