The inferential analysis of time-to-event endpoints (time to reach acceptable pain, time to reach no pain) will include summary, display, and analysis using Kaplan-Meier estimation method. The comparison of survival distributions between the group with patch and no-patch group will be done by the Log-Rank test. During the analysis, if the event if interest never occurs, the time will be censored at the final visit.

These analyses will be based on the ITT population, using the ITT paradigm (i.e. as randomized).

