3.3 General guideline for inferential analysis

All statistical tests will be conducted at 2-sided using 5% alpha level.

The inferential analysis of quantitative variables based on analysis of covariance (ANCOVA) model with the treatment group as fixed effect and baseline instantaneous pain NRS as a continuous covariate will be conducted with estimating and providing the Least-Square Means (LS Means), Standard Errors (SE) and 95% Confidence Intervals (CI) for each treatment group along with the LS Means, SE and 95% CI for the difference between treatment groups. Additional effects will be added to the model in case of need and described in CSR.

The inferential analysis of time-to-event endpoints will include summary, survival curves, and analysis using Kaplan-Meier estimation method. The comparison of survival distributions between treatment groups will be done by the Log-Rank test.

The inferential analysis of key secondary endpoints will be adjusted for multiplicity using a False Discovery Rate approach (Benjamini-Hochberg) within a separate analysis table that will consist nominal and adjusted p-values. Tables with original inferential key secondary analyses will be presented with the nominal p-values.

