5.1.7.2.1 Normalized Sum of Pain Intensity Difference

Pain Intensity Difference (PID) will be defined as instantaneous NRS change from baseline. The Sum of Pain Intensity Difference (SPID) will be calculated by multiplying the PID score at each post-baseline analysis timepoint by the duration (in hours) since the preceding timepoint. The Normalized SPID₀₋₅ will be calculated as the SPID over 5 days divided by the total duration time:

Normalized
$$SPID_{0-5} = \frac{\sum_{i=1}^{9} (T_i - T_{i-1}) * PID_i}{T_9 - T_0}$$
 ,

where $T_0 = 0$ (baseline), T_i – actual time (hours) from T_0 and PID_i – Pain Intensity Difference score at time Ti. Pain Intensity Difference, in turn, will be calculated as: $PID_i = PI_i - PI_0$, where PI_0 - Pain Intensity at time T_0 .

Normalized SPID₀₋₅ will be summarized with descriptive statistics for treatment groups and analyzed by ANCOVA model with the treatment group as fixed effect and baseline instantaneous pain NRS as a continuous covariate.

CONFIDENTIAL Page 20 of 30

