5.1.7.3.1 Time to Reach No Pain

Time to reach no pain (TTNP) will be defined as the time (hours) from baseline subject symptom self-assessment date and time (Day 1 Visit 1, Pain Perception) to the first report of instantaneous pain NRS=0. If that event never occurs, the time will be censored with the last evaluation of pain perception. If there are no post-baseline assessments collected, then the time will be censored with baseline subject symptom self-assessment.

TTNP will be listed and analyzed with cumulative distributions (F(t)) and the corresponding summaries using cumulative incidence estimates $(\hat{F}(t) = 1 - \hat{S}(t))$ based on the Kaplan-Meier survival estimates $(\hat{S}(t))$. The 95% confidence limits $(\hat{F}_L(t), \hat{F}_U(t))$ for point estimates will be evaluated using 95% confidence limits for survival estimates $(\hat{S}_L(t), \hat{S}_U(t))$ as follows:

$$\hat{F}_{L}(t) = 1 - \hat{S}_{U}(t); \ \hat{F}_{U}(t) = 1 - \hat{S}_{L}(t).$$

The comparison between treatment groups will be done by the Log-Rank test.

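### Time to acceptable pain, a key secondary endpoint, is compared by a log-rank test that makes no use of baseline NRS, and so gives up power to the extent that baseline NRS predicts the event

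*SAP*

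**What the plan says.** SAP 3.3 sets the rule for time-to-event endpoints: "The comparison of survival distributions between treatment groups will be done by the Log-Rank test". SAP 5.1.7.2.4 repeats it for time to acceptable pain ("The comparison between treatment groups will be done by the Log-Rank test"), and SAP 5.1.7.3.1 repeats it for time to no pain, which runs "to the first report of instantaneous pain NRS=0". Protocol 8.3.1.2 agrees: "The comparison of survival distributions between the group with patch and no-patch group will be done by the Log-Rank test". Neither document names strata, a covariate or a Cox model. SAP 5.1.11 records that the log-rank test was carried over unchanged from the protocol.

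The continuous endpoints are handled differently. SAP 3.3 specifies ANCOVA with "treatment group as fixed effect and baseline instantaneous pain NRS as a continuous covariate". The same covariate appears for SPID ("analyzed by ANCOVA model with the treatment group as fixed effect and baseline instantaneous pain NRS as a continuous covariate"), mobility, RMDQ, TOTPAR, and average, worst and least pain. SAP 3.3 also says "Additional effects will be added to the model in case of need and described in CSR", but that sentence stands in the ANCOVA paragraph and does not reach the log-rank test.

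Time to acceptable pain is a key secondary endpoint (protocol 6.3.2). Its p-value enters the Benjamini-Hochberg table and is read as confirmatory if the primary endpoint is significant (SAP 5.1.7.2.5). The p-value for time to no pain is descriptive only (protocol 8.3.1.5).

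**The concern.** Baseline instantaneous NRS is the plan's own choice of prognostic covariate. SAP 4.1.3 requires it for entry to the FAS, on which time to acceptable pain is analysed, so using it costs no subjects. The time-to-event comparison nevertheless ignores it, and no reason is given.

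If subjects who start with more pain take longer to call their pain acceptable, two things follow. A real effect is more likely to be missed than with a stratified or adjusted test. And if the arms happen to differ in baseline NRS, nothing in the analysis corrects for it, so the imbalance can move this p-value and, through the Benjamini-Hochberg step, the adjusted p-values of the other key secondary endpoints.

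Balance in the FAS cannot be taken for granted either. SAP 2.5 and protocol 7.3 name no stratification factor (protocol 7.3 refers to a separate randomization plan). The FAS also excludes subjects who used rescue medication after randomization, which may depend on pain level. Adjustment would not cure that selection, but it would account for the measured difference in NRS.

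**Working it through.** **The plan's own figure.** The only sample-size figure is for the primary responder endpoint: 90 evaluable per arm for 80% power at two-sided 5%, and 200 randomized with 10% dropout (SAP 2.4). By the pooled chi-square formula, the 20% vs 39% row gives n = [1.96·√(2·0.295·0.705) + 0.8416·√(0.2·0.8 + 0.39·0.61)]² / 0.19² = (1.264 + 0.531)² / 0.0361 = 89.3, so 90. The six rows need 81 to 90, and 180/0.90 = 200. The figure reproduces, but no event count, hazard ratio or power is stated for time to acceptable pain.

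**Inputs to the check.** From the documents: 90 per arm, two-sided 5%, and nine post-baseline assessments (the count in the SPID formula). Assumed: treatment hazard ratio (HR) 1.6; 75% or 50% of controls with an event by Day 5; exponential times over about 98 hours; baseline NRS 2 to 6 with probabilities 5, 15, 25, 30 and 25%; and event HR per NRS point from 1.0 (not prognostic) down to 0.5. Across NRS 1 to 6, an HR per point of 0.8, 0.7 or 0.6 means a hazard ratio of 1/0.8⁵ = 3.1, 1/0.7⁵ = 5.9 or 1/0.6⁵ = 12.9.

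**Anchor.** Events for 80% power at HR 1.6: 4·(1.96 + 0.8416)² / (ln 1.6)² = 31.4/0.2209 = 142.1, so 143. With NRS not prognostic and 75% control events, the simulation produced about 148 events. The expected power is then Φ(0.470·√148/2 − 1.96) = Φ(0.90), or 82%, which agrees with the first row below.

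**Power, 75% control events, 5,000 runs** (stratified by each NRS score):

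| Event HR per NRS point | Plain log-rank | Stratified log-rank | Difference (points) |
|---|---|---|---|
| 1.0 | 82.1% | 80.5% | −1.6 |
| 0.8 | 76.9% | 78.0% | +1.1 |
| 0.7 | 73.2% | 78.4% | +5.2 |
| 0.6 | 63.9% | 76.4% | +12.5 |

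The Monte Carlo standard error of one power figure is about √(0.78·0.22/5000) = 0.6 points. At HR 0.5 (1,500 runs) the figures were 55.7% and 76.9%. With 50% control events (1,500 runs), plain vs stratified was 65.5/64.9, 64.9/64.7, 60.5/65.7, 53.6/62.7 and 48.3/64.1% at 1.0, 0.8, 0.7, 0.6 and 0.5. A Cox model with NRS as covariate was within about 2 points of the stratified test.

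**Type I error (75% control events, 5,000 runs).** Overall it was 4.5 to 5.4% for the plain test and 4.3 to 5.3% for the stratified test. The SD of the between-arm difference in mean NRS is 1.16·√(2/90) = 0.173, so an imbalance above 1.5 SD is about 0.26 points. Among runs with such an imbalance (634 to 697 of 5,000), the plain test rejected in 6.0, 7.6 and 11.6% at HR per point of 0.8, 0.7 and 0.6, against 4.1, 5.0 and 6.3% when stratified. At 6% with 634 runs the standard error is about 0.9 points, so the excess at 0.8 is not distinguishable from 5%.

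**Two strata only.** A second simulation used NRS 1 to 6 (weights 5, 10, 20, 20, 25, 20%; mean 4.1, SD √(18.9 − 16.81) = 1.45), with 90 per arm and the effect set so that the plain test had about 80% power. Its log-hazard slopes of 0.40 and 0.74 per SD are HRs per point of exp(−0.40/1.45) = 0.76 and exp(−0.74/1.45) = 0.60. Stratifying by NRS 1–3 vs 4–6 gained 2.3, 3.2 and 4.4 points at 0.76, and 7.2, 9.3 and 11.4 points at 0.60, for 30, 50 and 70% control events.

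**The case against.** The strongest reply is that nothing here is wrong. The log-rank test is pre-specified in both documents, was kept deliberately, and holds its error rate. The plan also follows a pattern: linear models take the covariate, while binary and time-to-event endpoints get standard unadjusted tests, including Fisher's exact test for the primary. That explains the choice. It does not remove the gain from using a value already in hand.

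Three further limits stand.

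- A reader might infer that subjects who start at NRS 1 or 2 are only a point or two from the event. That holds for time to no pain, which is descriptive. Acceptable pain is a yes/no judgement (protocol 7.6.2), not an NRS threshold, and it is not asked at Visit 1. Some link with baseline NRS is plausible, but the documents do not show its strength.
- A reader might infer a gain of 10 to 15 points from an adjusted Cox model. That size appears in the second simulation only at an HR of 0.60 per point, roughly a 13-fold difference in hazard between NRS 1 and 6, and with data generated from the proportional-hazards, log-linear model that the Cox analysis assumes. It is a favourable case.
- The FAS is not 90 per arm, because rescue users are excluded. Nor is the NRS range certain to be 1 to 6: the SAP revision history mentions revised enrolment criteria, and SAP 5.1.2 splits demographics by protocol version.

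Stratified randomization by NRS cannot be ruled out, because the randomization plan is not part of the documents. It would limit imbalance, but it would not bring NRS into the analysis.

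**Conclusion.** The point holds as a cheap improvement to one key secondary analysis. The unadjusted log-rank test is valid. A reader might infer an inflated error rate or a biased treatment effect, but the overall type I error is about 5%. The weaker marginal hazard ratio that arises when a covariate is left out reflects non-collapsibility, not bias, and the SAP reports no hazard ratio. The exposure to imbalance is conditional on a chance difference in baseline NRS.

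The size depends on an association that the documents do not give. The change in power runs from a loss of 1 to 2 points if baseline NRS is not prognostic, through about +1 and +5 points at HRs of 0.8 and 0.7 per point, to about +12 at 0.6. These figures assume 90 per arm, a treatment HR of 1.6, 75% control events and proportional hazards. The case rests on time to acceptable pain; time to no pain adds little.

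**What to change.** Before database lock, amend SAP 3.3 and 5.1.7.2.4 as follows:

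- Compare time to acceptable pain by a log-rank test stratified by baseline instantaneous NRS. Use categories that cover every value in the FAS, for example 3 or below vs 4 or above, and take this p-value into the Benjamini-Hochberg table.
- Report a hazard ratio with 95% CI from a Cox model with treatment group and continuous baseline NRS as the supporting effect estimate, with Efron handling of ties. The plan now gives no between-arm estimate for this endpoint.
- Keep the cumulative incidence curves, and show the unadjusted log-rank test as supportive.
- Make the same change in SAP 5.1.7.3.1 for consistency only, and list the change in SAP 5.1.11.

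The cost is SAP wording and a few lines of code. No new data are needed and no FAS subject is lost. The downside is 1 to 2 points of power if baseline NRS is not prognostic. Two broad strata may also recover less than strata by single score. The Cox estimate assumes proportional hazards and a linear NRS effect; the stratified test does not need the linear form. If the database is already locked, the stratified result should be labelled post hoc and the planned test left in the table.

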5.1.7.2.5 Adjustments for Multiple Testing

The multiplicity of key secondary endpoints will be handled using a False Discovery Rate approach (Benjamini-Hochberg) within a separate analysis table that will consist nominal and adjusted p-values. Tables with original inferential key secondary analyses will be presented with the nominal p-values.

p-values from key secondary endpoints analyses will be interpreted in a confirmatory way only in case the primary endpoint was statistically significant. Otherwise, they will be interpreted as exploratory.

CONFIDENTIAL Page 21 of 30

The final approach will be specified in the footnote of the table with multiplicity adjustment depending on the results of primary endpoint analysis.

5.1.7.3 Other Secondary Analyses

Other Secondary Analyses will be based on the FAS population.

5.1.7.3.1 Time to Reach No Pain

Time to reach no pain (TTNP) will be defined as the time (hours) from baseline subject symptom self-assessment date and time (Day 1 Visit 1, Pain Perception) to the first report of instantaneous pain NRS=0. If that event never occurs, the time will be censored with the last evaluation of pain perception. If there are no post-baseline assessments collected, then the time will be censored with baseline subject symptom self-assessment.

TTNP will be listed and analyzed with cumulative distributions (F(t)) and the corresponding summaries using cumulative incidence estimates $(\hat{F}(t) = 1 - \hat{S}(t))$ based on the Kaplan-Meier survival estimates $(\hat{S}(t))$. The 95% confidence limits $(\hat{F}_L(t), \hat{F}_U(t))$ for point estimates will be evaluated using 95% confidence limits for survival estimates $(\hat{S}_L(t), \hat{S}_U(t))$ as follows:

$$\hat{F}_{L}(t) = 1 - \hat{S}_{U}(t); \ \hat{F}_{U}(t) = 1 - \hat{S}_{L}(t).$$

The comparison between treatment groups will be done by the Log-Rank test.

5.1.7.3.2 Time Course of Pain Intensity Difference

PID score will be summarized with descriptive statistics by treatment group and by analysis timepoint. Additionally, box plots of mean PID scores will be presented graphically by treatment group and by analysis timepoint. The specified figure will be supported by a corresponding summary table.

5.1.7.3.3 Time Course of Pain Relief

Pain Relief score will be summarized with descriptive statistics by treatment group and by analysis timepoint. Additionally, box plots of mean pain relief scores will be presented graphically by treatment group and by analysis timepoint. The specified figure will be supported by a corresponding summary table.

5.1.7.3.4 Normalized Sum of Pain Relief

Total pain relief (TOTPAR) will be calculated by multiplying the pain relief score (0='none', 1='slight', 2='moderate', 3='lots', 4='complete') at each post-baseline analysis timepoint by the duration (in hours) since the preceding timepoint. The Normalized Sum of Pain Relief over 5 days (TOTPAR $_{0-5}$) will be calculated as the TOTPAR divided by the total duration time.

Normalized TOTPAR₀₋₅ =
$$\frac{\sum_{i=1}^{9} (T_i - T_{i-1}) * PAR_i}{T_9 - T_0},$$

CONFIDENTIAL Page 22 of 30

Private and Confidential Study No LPS16453 Date: DEC 12, 2022

where $T_0 = 0$, T_i – actual time and PAR_i – pain relief score at time T_i .

Normalized TOTPAR₀₋₅ will be summarized with descriptive statistics for treatment groups and analyzed by ANCOVA model with the treatment group as fixed effect and baseline instantaneous pain NRS as a continuous covariate.

5.1.7.4 Exploratory Analyses

5.1.7.4.1 Pain Perception – Average Pain, Worst Pain and Least Pain

Pain Perception, including NRS of Average Pain, Worst Pain and Least Pain, will be summarized for actual values and change from baseline with descriptive statistics for FAS population by treatment group and by analysis timepoint (from Baseline to Day 5 Visit 2).

Change from baseline for NRS of Average Pain, Worst Pain and Least Pain at Day 5 Visit 2 will be analyzed by ANCOVA model with the treatment group as fixed effect and baseline instantaneous pain NRS as a continuous covariate.

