7.6 Clinical Procedures

The study will be performed in Investigational Sites and an online e-diary will be used.

A total of 2 site visits and 1 phone contact are planned during a maximum of 5 days of treatment and 6 days of total study duration.

7.6.1 Day 1, Visit 1

Clinical procedures on Day 1, Visit 1 include the following:

- Verification of eligibility
- Informed Consent Signatures
- Local Physical Examination

- Collection of Vital Signs to include: Respiratory rate, Heart rate, Temperature, Blood Pressure
- Collection of Demographics to include: Age, Gender
- Collection of relevant medical history and concomitant medications
- On-line daily e-diary will be explained and activated
- Urine pregnancy testing (for women of childbearing potential only)
- Causes and/or circumstances triggering the acute back pain
- Baseline Subject symptom self-assessment
 - Pain Perception (NRS): Numerical Rating Scale^[3] for pain assessments at baseline and at defined time points: 0-10 NRS; '0' representing "no pain" and '10' representing "worst pain imaginable
 - Instantaneous: pain at the moment of the evaluation
 - Average pain in the previous 12 hours.
 - Worst pain in the previous 12 hours
 - Least pain in the previous 12 hours
 - o Roland-Morris Disability Questionnaire (RMDQ)^[5]
- Baseline mobility assessment (physician)
- Randomization:
 - O Arm A: ITP FIRTECH: Patch application according to the instruction for use in Section 17.3: The patch has to stay in position for 5 days. If the patch is taken-off or if it fell off during the study duration, the subject is invited to replace the patch at home following the instruction for use. Subject is allowed to take-off the patch at any time in case of severe skin itchiness, irritation, or skin reaction and in this case the subject has to contact the study center.
 - o Arm B: no-patch: Subjects will be informed that they will not be assigned a patch in this study.
- All subjects are informed that rescue mediation (paracetamol, up to 2 g per day), while not encouraged, is allowed if necessary.
- All subjects will be informed of the prohibited medications.
- If rescue medication is taken, the exact moment(s) and the dose(s) have to be indicated in the e-diary.
- An explanation will be provided on how to use e-diary at home and providing all necessary access credentials
- All subjects will be requested to avoid bed rest and will be recommended to continue with a normal daily life activity.

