8.3.1.2 Secondary Analyses

Under the secondary analyses (key and other), descriptive and inferential analysis, where applicable, will be conducted for the following:

- Normalized Sum of Pain Intensity Difference (SPID₀₋₅): the descriptive and inferential analyses will be conducted for Day 5.
- Roland-Morris Disability Questionnaire^[5] (RMDQ) score: descriptive analysis will be conducted for the observed values at baseline and Day 5, as well as for change (improvement (%)) from baseline to Day 5. Inferential analysis will be conducted for change (improvement (%)) from baseline to Day 5.
- Mobility evaluation^[6,7]: descriptive analysis will be conducted for the observed values at baseline and Day 5, as well as for change from baseline to Day 5. Inferential analysis will be conducted for change from baseline to Day 5.
- Time to reach acceptable pain and time to reach no pain: descriptive and inferential analysis will be conducted based on the data obtained in between baseline and final visit assessments.
- Normalized Sum of Pain relief (TOTPAR₀₋₅): the descriptive and inferential analyses will be conducted for Day 5.
- Time course of PID and time course of Pain relief (VRS): descriptive analysis will be conducted for the observed values from baseline to Day 5.
- Frequency of Adverse Events: descriptive analysis will be conducted based on the data obtained in between baseline and final visit.

The inferential analysis for the Normalized Sum of Pain Intensity Difference (SPID₀₋₅), Roland-Morris Disability Questionnaire^[5] (RMDQ) score, Mobility evaluation^[6,7], Normalized Sum of Pain relief (TOTPAR₀₋₅), will be based on the analysis of covariance (ANCOVA) model with the group (patch, no-patch) as fixed effect and baseline pain intensity as a continuous covariate. The Least-Square Means, Standard Errors and 95% Confidence Intervals for each group (patch, no-patch) will be estimated and provided, along with the Least-Square Means, Standard Errors and 95% Confidence Intervals for the difference between group with patch and no-patch group. Additional effects will be added to the model in case of need.

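### The three exploratory ANCOVAs of average, worst and least pain adjust for baseline instantaneous pain only, so imbalance in each item's own baseline is only partly corrected and precision may be lost

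*SAP*

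**What the plan says.** SAP 5.1.7.4.1 sets the inferential analysis of the three recall items: "Change from baseline for NRS of Average Pain, Worst Pain and Least Pain at Day 5 Visit 2 will be analyzed by ANCOVA model". The model is fitted "with the treatment group as fixed effect and baseline instantaneous pain NRS as a continuous covariate". SAP 3.3 makes the same covariate the default for every ANCOVA in the plan.

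Protocol 7.6.1 lists four separate NRS items at Day 1, Visit 1, under "Baseline Subject symptom self-assessment". One is pain at the moment of evaluation. The others are "Average pain in the previous 12 hours", "Worst pain in the previous 12 hours" and "Least pain in the previous 12 hours". Each analysed item therefore has its own Visit 1 value, and SAP 5.1.7.4.1 needs that value to form the change score.

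Protocol 8.3.1.2 describes the covariate for the secondary ANCOVAs as "baseline pain intensity as a continuous covariate". Protocol 8.3.1.3 says that worst, least and average pain will be handled in a similar way. Neither document puts the analysed item's own baseline in the model. Both allow further effects to be added if needed, without naming any.

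**The concern.** For SPID the covariate matches the outcome, because both rest on instantaneous pain. For the three recall items it does not: the outcome is change in pain over the previous 12 hours, and the covariate is pain at one moment. The two can differ. SAP 4.1.2 and 4.1.3 provide for randomized subjects whose baseline instantaneous score is 0 in a trial of acute low back pain.

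A change score that is not adjusted for its own baseline keeps some regression to the mean. Take a subject whose worst pain was high in the 12 hours before Visit 1 but whose pain at the visit was low. That subject will tend to show a large fall that the instantaneous baseline does not explain. This adds residual variance. If the arms differ by chance in baseline worst pain, part of the difference reaches the estimated effect.

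At stake are the estimates and intervals that answer the exploratory objective on least, average and worst pain (Protocol 5.3, SAP 2.1.3). No confirmatory result is involved.

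**Working it through.** **The plan's own figure.** Neither document gives a power or precision figure for these models. The only sample-size statement is for the primary responder endpoint, 90 evaluable subjects per group for 80% power. It does not bear on this point.

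**Inputs.** The documents give no SD or correlation for these items, so the following are assumptions:
- ρ: correlation of the item's baseline with its Day 5 value, 0.3 to 0.6
- c: correlation of the item's baseline with the instantaneous baseline, 0.5 to 0.8
- s: baseline SD divided by Day 5 SD, taken first as 1 and then lower
- the instantaneous baseline is related to Day 5 only through the item's own baseline

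**Formulas**, with the Day 5 SD set to 1:
- Residual variance of the change given the item's own baseline: V_own = 1 − ρ²
- Residual variance of the change given the instantaneous baseline: V_plan = 1 + s² − 2ρs − c²(s − ρ)² = (1 − ρ²) + (1 − c²)(s − ρ)²
- Cut in residual variance: 1 − V_own/V_plan
- Power with the own baseline, if the planned model has 80%: Φ(2.8016 × √(V_plan/V_own) − 1.96)

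**Equal SDs (s = 1):**

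| ρ | c | V_plan | V_own | Cut | 80% power becomes |
|---|---|---|---|---|---|
| 0.3 | 0.5 | 1.2775 | 0.91 | 28.8% | 91% |
| 0.3 | 0.8 | 1.0864 | 0.91 | 16.2% | 86% |
| 0.5 | 0.5 | 0.9375 | 0.75 | 20.0% | 88% |
| 0.5 | 0.7 | 0.8775 | 0.75 | 14.5% | 86% |
| 0.5 | 0.8 | 0.8400 | 0.75 | 10.7% | 84% |
| 0.6 | 0.5 | 0.7600 | 0.64 | 15.8% | 86% |
| 0.6 | 0.8 | 0.6976 | 0.64 | 8.3% | 83% |

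**Smaller baseline SD**, at ρ = 0.5 and c = 0.7, where V_own = 0.75:
- s = 0.8: V_plan = 0.75 + 0.51 × 0.09 = 0.7959; cut 5.8%; 80% power becomes 82%
- s = 0.7: V_plan = 0.75 + 0.51 × 0.04 = 0.7704; cut 2.6%
- s = 0.5: V_plan = 0.75 + 0.51 × 0 = 0.75; cut zero

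**Imbalance, equal SDs.** If the arms differ by one point in the item's baseline, the expected shift in the estimated difference is:
- no covariate: −(1 − ρ)
- planned covariate: −(1 − ρ)(1 − c²)
- own baseline: 0

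The planned covariate thus removes a share c² of the shift. At ρ = 0.5 and c = 0.7 the shift goes from −0.50 to −0.5 × 0.51 = −0.255, so 49% is removed. At c = 0.8, 64% is removed.

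**Simulation.** In 10,000 simulated trials of 90 per arm at ρ = 0.5, c = 0.7 and s = 1, the shift per point was −0.27 under the planned model and −0.01 with the own baseline. The variance ratio of the two estimates was 1.20, against 0.8775/0.75 = 1.17 from the formula. Both estimates averaged approximately zero when the true effect was zero.

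**The case against.** **One common, pre-specified covariate is a valid choice, and these endpoints carry little weight.** This stands. Protocol 6.3.3 and SAP 2.2.3 list them as descriptions of worst, least and average pain. Protocol 8.3.1.5 gives their p-values for description only, and they lie outside the false-discovery-rate family. They have no power target, so the power figures above only express precision on a familiar scale.

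**The gain may be negligible.** This also stands. Entry is capped at NRS 6 (without naming the item), and the FAS drops subjects with a baseline instantaneous score of 0, while Day 5 scores can span 0 to 10. A baseline SD below the Day 5 SD is plausible, and the gain then falls quickly. The documents cannot settle whether the instantaneous baseline predicts Day 5 only through the item.

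**Further effects may be added in case of need (Protocol 8.3.1.2, SAP 3.3).** This does not answer the point. The clause names no covariate and leaves the choice until after open-label data have been seen.

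A reader might infer that the SAP narrowed the protocol's covariate. The documents do not support that. Protocol 6.3.2 defines the pain intensity difference as change in the instantaneous NRS, so baseline pain intensity in Protocol 8.3.1.2 most naturally means the instantaneous item. Protocol 8.3.1.3 carries that approach to the recall items, and the SAP follows it.

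A reader might also infer that imbalance in the item goes uncorrected. That is too strong: the correlated covariate removes part of it, and SAP 5.1.7.4.1 tabulates baseline values by arm, so an imbalance would be visible.

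**Conclusion.** The point holds as an efficiency improvement to three exploratory models. The covariate is a different item from the outcome, the matching baseline is collected, and nothing in the plan puts it in the model. Chance imbalance in the item's own baseline is corrected only by roughly a share c².

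The loss of precision is possible but not established. It is about 8% to 29% of residual variance under equal SDs with ρ of 0.3 to 0.6 and c of 0.5 to 0.8. It is about 6% at an SD ratio of 0.8, and zero at 0.5, with ρ = 0.5 and c = 0.7. All of these rest on assumed values. It would be wrong to state as fact that the planned intervals are wider than the data allow.

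Nor does the choice of covariate make the estimate biased on average: chance imbalance at randomization averages out, and the cost is precision and sensitivity to the imbalance in the trial at hand. The FAS excludes post-randomization rescue users, which may cause baseline differences that are not purely chance. That is a separate matter, which own-baseline adjustment would not cure.

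The primary conclusion and the sample size are unaffected. The change is desirable, not essential.

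**What to change.** In SAP 5.1.7.4.1, add the baseline value of the item being analysed as a continuous covariate: baseline average pain for average, baseline worst for worst, baseline least for least. Baseline instantaneous NRS can stay as a second covariate if a common term across models is wanted. In that two-covariate form, the added term cannot raise the population residual variance, whatever the correlations and SDs.

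The cost is one sentence in the SAP, one extra term in three models and one degree of freedom in each. No new data are needed, and no subjects are lost, because the change score already requires the item's own baseline.
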